14.1.2 Secondary Endpoints

Secondary endpoints include progression-free survival (PFS), overall survival (OS), and toxicity. Toxicity will use the CTCAE 4.0 and will summarize the worst grade per toxicity, per patient.

Additional secondary endpoints relate to biological correlates, including E-Selection, IL-6, the pre-metastatic niche density, pSTAT3, and baseline HGF. Because the nature of these secondary endpoints is exploratory, we will not consider the issue of multiple comparisons and the according adjustment of p-values.

To determine an association between E-selectin, IL-6 and pre-metastatic niche density, we will conduct a pairwise correlation test (linear regression). When the sample size is 28, the linear regression test of rho=0 (alpha = 0.050 one-sided) for one normally distributed covariate will have 80% power to detect a correlation coefficient of 0.435.

To determine if the biological correlates (e.g, IL-6, E-selectin, pSTAT3, and HGF), are associated with progression-free survival (PFS), we will fit univariate or multivariate Cox proportional hazards model and report the corresponding p-values. The same method will be employed to evaluate the prognostic effect of pre-metastatic niches.

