1.2 Secondary Objectives

- 1.2.1 To determine if baseline HGF, E-selectin and IL-6 are associated with PFS
- 1.2.2 To determine if pre-metastatic niche density in regional LNs is associated with PFS
- 1.2.3 To determine an association between E-selectin, IL-6 and pre-metastatic niche density
- 1.2.4 To evaluate the prognostic effect of pre-metastatic niches as an independent factor in time to first relapse
- 1.2.5 To determine if pSTAT3 in tumor tissue is associated with PFS
- 1.2.6 To describe the toxicity associated with pazopanib in this patient population
- 1.2.7 To evaluate PFS and OS
- 1.2.8 To compare, within patient, time to tumor progression of 2nd-line therapy with time to tumor progression on pazopanib as 3rd-line therapy

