4.1.2 Assessments within 7 days of the first dose

- 4.1.2.1 Physical examinations: height (only recorded at baseline) and body weight and current medical conditions.
- 4.1.2.2 Vital signs: body temperature, blood pressure and heart rate.

Note: If a subject presents with poorly controlled hypertension, defined as SBP \geq 140mmHg or DBP \geq 90mmHg, antihypertensive medication(s) should be initiated or adjusted with a goal to control the blood pressure to $<140/90$ mmHg.

- 4.1.2.3 ECOG PS
- 4.1.2.4 Clinical laboratory assessments.
- 4.1.2.5 12-lead ECG with QTc measurement
- 4.1.2.6 Baseline IL-6 and E-selectin assessment
- 4.1.2.7 Serum pregnancy test for women of childbearing potential.

4.1.3 Pre-dose Assessments on Day 1

- 4.1.3.1 Physical examination: to identify any changes in the subject's mental and medical conditions since baseline assessment that would make him/her ineligible for the study.
- 4.1.3.2 Blood pressure measurements: subjects must have a blood pressure reading of <140/90mmHg to be eligible.
- 4.1.3.3 ECOG PS: Any changes since baseline assessment should be recorded in the eCRF. Subjects having deterioration of ECOG PS to ≥ 2 will be excluded from the study
- 4.1.3.4 Review results of all the other baseline assessments to determine the subject's eligibility for the study. Any screening laboratory results outside the normal range will be repeated (prior to the first dose) at the discretion of the Investigator. All laboratory results must be within the values outlined in the Inclusion Criteria before the first dose of study drug.
- 4.1.3.5 Record all the medication(s) received within 2 weeks prior to the first dose of study medication and indicate if the medication is continuing.
- 4.1.3.6 Obtain archived tumor tissue samples for biomarker assessments (if available).
- 4.1.3.7 Obtain a blood sample for biomarker research. It is preferable to collect the sample on the first day of dosing but the sample may be collected at any time after first dose of investigational product. **Note:** a signed written informed consent for participating biomarker research must be obtained before collecting the blood sample for biomarker analysis.

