10.1.2 Measurement of pre-metastatic niche density and pSTAT3

If patient consent is obtained, a total of 12 unstained slides derived from tumor and 12 unstained slides derived from normal lymph node tissue will be requested. Normal lymph node tissue will be assessed for pre-metastatic niche density, characterized as the number of clusters of VEGFR1⁺VLA-4⁺ cells per x 100 objective field.²⁹ This assessment will be performed through previously defined techniques.

pSTAT3 will be measured in paraffin-embedded sections. The authors of the protocol understand that collection procedures for specimens in this retrospective analysis are not standardized, and this may lead to inherent variability in pSTAT3 levels. Acknowledging this potential caveat, we would like to measure pSTAT3 and determine the relationship of this activated moiety to PFS. pSTAT3 will be determined through previously reported techniques.²⁴

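### The 80% power at a correlation of 0.435 holds only for a fixed covariate; for the normally distributed covariate the plan names it is about 77%, and lower if the test is two-sided or node tissue is short

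*Combined protocol and SAP*

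**What the plan says.** Secondary objective 1.2.3 reads "To determine an association between E-selectin, IL-6 and pre-metastatic niche density". It gives no sign for any of the associations. For this aim Section 14.1.2 says "we will conduct a pairwise correlation test (linear regression"). Read literally, that covers three pairs: IL-6 with niche density, E-selectin with niche density, and IL-6 with E-selectin.

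The power statement follows in the same paragraph. It is conditional ("When the sample size is 28"), and it declares its level, sidedness and result together: "alpha = 0.050 one-sided) for one normally distributed covariate will have 80% power to detect a correlation coefficient of 0.435". Section 14.1.2 also calls the biological correlates exploratory and waives multiplicity adjustment.

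On tissue, Section 2.8 says the niche is assessed in regional nodes removed at nephrectomy. Section 10.1.2 makes its request for slides conditional: "If patient consent is obtained, a total of 12 unstained slides derived from tumor and 12 unstained slides derived from normal lymph node tissue". No inclusion criterion in Section 3.1 requires a nephrectomy or available node tissue, and no expected number with evaluable nodes is given.

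For the same question, the Statistical Considerations part of the synopsis names a t-test instead of a correlation.

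**The concern.** Three features of the statement make it look more favourable than the planned analysis.

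- **Model.** IL-6, E-selectin and niche density are all measured on patients, and the sentence itself calls the covariate normally distributed. A power formula that holds the covariate values fixed does not match that description.
- **Sidedness.** A one-sided test serves an aim that has no stated direction.
- **Number evaluable.** The full trial size is used for pairs that need stored node tissue, which some patients may not have.

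At stake is how a null result is read. Section 2.8 puts the niche forward as a possible explanation of the prognostic role of IL-6 and E-selectin. A non-significant correlation judged against 80% power at 0.435 would look like fair evidence against that idea. Judged against the power actually available, it would be weaker evidence.

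**Working it through.** **Inputs.** From Section 14.1.2: n = 28, ρ = 0.435, α = 0.05 one-sided, test of ρ = 0 by linear regression. From Section 14.1.1: first-stage size 14.

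**1. The plan's own figure (covariate fixed).** The slope t-test has n − 2 = 26 degrees of freedom and noncentrality √n · ρ/√(1 − ρ²).
- 0.435² = 0.1892; √(1 − 0.1892) = 0.9004; 0.435/0.9004 = 0.4831
- √28 = 5.2915, so the noncentrality is 5.2915 × 0.4831 = 2.556
- One-sided power from the noncentral t: 80.07%. The ρ giving exactly 80% is 0.4347.

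The stated figure reproduces, so this is evidently how it was obtained.

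**2. Random normal covariate.** Given the covariate values, the noncentrality is √S · ρ/√(1 − ρ²), where S is the standardised sum of squares about the mean. For a normal covariate S follows a chi-square distribution on n − 1 degrees of freedom, and power is the average over that distribution.
- Replacing 28 by the mean of S, which is 27, already gives 78.8%.
- Averaging over the whole distribution gives 76.9%. Simulation gives 76.8% to 77.0%.
- Cross-check by Fisher's z: atanh(0.435) × √25 = 0.4660 × 5 = 2.330; 2.330 − 1.645 = 0.685; power 75.3%, or 76.6% with the bias term.
- 80% power needs ρ = 0.451, or n = 31 at ρ = 0.435.

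**3. Two-sided 5% test, random covariate, n = 28.** Power at 0.435 is 66.0% (69.2% even with a fixed covariate). 80% power needs ρ = 0.500, or n = 39 at ρ = 0.435.

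**4. Fewer evaluable nodes (niche-density pairs only).** The smaller sizes are assumptions, because the documents give no yield. Random-covariate results:

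| n | Power at 0.435, one-sided | Power at 0.435, two-sided | ρ for 80% power, one-sided | ρ for 80% power, two-sided |
|---|---|---|---|---|
| 28 | 76.9% | 66.0% | 0.451 | 0.500 |
| 20 | 63.2% | 50.2% | 0.526 | 0.579 |
| 14 | 48.7% | 35.6% | 0.614 | 0.671 |

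Fourteen is also the first-stage size. Stopping there requires no responders: 0.92¹⁴ = 31% at a true response rate of 8%, but only 0.77¹⁴ = 2.6% at 23%. Low tissue yield and early stopping are separate routes to a small n, and the table is not a forecast of either.

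**The case against.** Several stronger readings are tempting, and the documents do not support them.

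- **That the 80% is a calculation error.** It is not. The plan names a linear regression test, and the figure is correct for that test with the covariate held fixed. The mismatch is with the description of the covariate and costs about 3 points.
- **That the test really runs at 10%.** That would follow only if the direction were chosen after seeing the data, and nothing in the plan says so. One-sidedness is openly declared. Section 2.8 also implies a positive direction for the niche pairs, since it describes IL-6 and E-selectin as promoting the niche. What stands is that Section 14.1.2 never writes the direction down, and that none is evident for IL-6 with E-selectin.
- **That true power is 66%.** That is the power of a two-sided test, which is not the test planned. It applies only if the undirected objective is tested as worded.
- **That the plan assumes nodes from all 28 patients.** The sentence is conditional on 28. Nor is 28 a strict ceiling: Section 6.5 replaces under-treated patients, and Section 3.3 allows accrual to expand.
- **That tissue limits all the correlations.** IL-6 with E-selectin needs only blood, and a baseline assessment is scheduled (Section 4.1.2.6).
- **That Section 4.1.3.6 shows node tissue is optional.** Its wording, "Obtain archived tumor tissue samples for biomarker assessments (if available"), concerns tumor tissue. The node argument rests on Sections 2.8, 3.1 and 10.1.2.

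It is also fair to say that the trial's size comes from the two-stage response design, and that no decision depends on this sentence.

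**Conclusion.** The point holds, at minor severity. Under the plan's own description of the covariate, the stated power is too high by about 3 percentage points. This part needs no assumption beyond bivariate normality.

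The missing direction is a gap in specification. It costs power (to about two in three at 0.435) only if the undirected aim is tested two-sided at 5%.

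For the two niche-density pairs the shortfall in tissue is probably the largest effect, but its size cannot be derived from the documents. The results at 20 and 14 patients illustrate what happens if the yield is of that order; the true number could lie outside that range. The primary endpoint and its design are untouched.

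**What to change.** Revise the paragraph in Section 14.1.2 as follows.

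1. Restate the power for a random normal covariate: about 77% at 0.435, or 80% at about 0.45, one-sided with n = 28.
2. Either state the expected direction for each pair in advance, or use a two-sided 5% test with a detectable correlation of about 0.50 at n = 28.
3. For the niche-density pairs, state the expected number with evaluable nodes and the detectable correlation at that number. If no estimate exists, show two-sided values of about 0.50, 0.58 and 0.67 at n = 28, 20 and 14, labelled as assumed sizes.
4. Report a 95% confidence interval with each correlation, so that a null result shows which values remain compatible with the data.
5. Reconcile the section with the synopsis. If the t-test there means the test of the regression slope, say so; if it means a comparison of two groups, define the groups or drop it.

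The cost is a change of wording, with no effect on sample size, patients or conduct. The downside is a less favourable stated figure.

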14.2 Sample Size Accrual Rate

The previously noted sample size of 28 patients is anticipated to accrue over the course of 12 months.

15.0 Human Subject Issues

15.1 Institutional Review Board

In accordance with federal regulations, an Institutional Review Board (IRB) that complies with regulations at 45 CFR 46 and 21 CFR 50, 56 must review and approve this protocol and the informed consent form prior to initiation of the study. All institutional, NCI, Federal, and State of California regulations must be fulfilled.

15.2 Recruitment of Subjects

Patients with mRCC will be recruited from patients undergoing evaluation and treatment at City of Hope Cancer Center for this diagnosis.

15.3 Advertisements

Advertisements to include print, media (radio, television, billboards), telephone scripts, etc., will be reviewed and approved by the IRB prior to their use to recruit potential study subjects.

15.4 Study location and Performance Sites

This study will be performed at COH.

15.5 Confidentiality

This research will be conducted in compliance with federal and state of California requirements relating to protected health information (PHI).

15.6 Financial Obligations and Compensation

If there is a serious medical complication of the research, treatment will be available at City of Hope, but there will be no compensation to the subject for this injury.

15.7 Informed Consent Processes

The Principal Investigator or IRB approved named designate will explain the nature, duration, purpose of the study, potential risks, alternatives and potential benefits, and all other information contained in the informed consent document. In addition, they will advise the research subjects about their rights and the HIPAA research authorization form. Research subjects will be informed that they may withdraw from the study at any time and for any reason without jeopardizing, include as applicable, their future care or their employment at City of Hope or any relationship they have with City of Hope.

Should sufficient doubt be raised regarding the adequacy of comprehension, further clarifications will be made and the questionnaire repeated until a satisfactory result is obtained. Prospective research subjects who cannot adequately comprehend the fundamental aspects of the research study with a reasonable amount of discussion, education and proctoring will be ineligible for enrollment. Following this procedure, the research team will review the results of eligibility testing and determine if the research subject is a candidate for study enrollment.

17.0 Appendix I: Urine Protein Creatinine Ratio (UPC)

Clinical meaning of UPC

There is a good correlation between the ratio of protein concentration to creatinine concentration in a random urine sample and the amount of protein excreted over 24 hours. Creatinine excretion is fairly constant throughout the day regardless of changes in urine flow rate.

Men excrete 20 mg to 25 mg of creatinine/kg of body weight/day.

Women excrete 15 mg to 20 mg of creatinine/kg of body weight/day.

Normal protein excretion is <100 mg to 150 mg/24 hours and is similar for men and women.

Calculating UPC

UPC ratio = Urine protein (mg/dL) / Urine creatinine (mg/dL).

UPC ratio \approx equivalent to grams of protein excreted in urine over 24 hrs.

Example: Patient has a urine protein = 90 mg/dL and urine creatinine = 30 mg/dL.

UPC ratio = $(90 \text{ mg/dL}) / (30 \text{ mg/dL}) = 3$

The calculated UPC ratio is 3, which correlates to roughly 3 g protein excretion in a 24-hour period.

Units for UPC ratio

Note: To calculate UPC, protein and creatinine concentrations must be expressed in the same units (mg/dL, g/L, or $\mu\text{mol/L}$). If, for example, protein concentration is expressed in mg/dL and creatinine concentration is expressed in $\mu\text{mol/L}$, conversion of one of the concentration values is required. Conversion factors are:

From	To	Conversion Factor
Conventional Units: mg/dL	SI Units: $\mu\text{mol/L}$	Multiply by 88.4
SI Units: $\mu\text{mol/L}$	Conventional Units: mg/dL	Divide 88.4

References:

NKF: NKF KDOQI Guidelines [Internet]. National Kidney Foundation; nd. KDOQI Clinical Practice Guidelines for Chronic Kidney Disease: Evaluation, Classification, and Stratification. Available from http://www.kidney.org/professionals/KDOQI/guidelines_ckd/p5_lab_g5.htm

Appendix II: Determination of Creatinine Clearance (Cl_{CR})

Estimation of creatinine clearance using Cockcroft and Gault method:

$$\text{Cl}_{\text{CR}} \text{ for males (mL/min)} = \frac{[140 - \text{age (years)}] \times [\text{weight (kg)}]}{(72) \times [\text{Serum creatinine (mg/dL)}]}$$

$$\text{Cl}_{\text{CR}} \text{ for females (mL/min)} = \frac{(0.85) \times [140 - \text{age (years)}] \times [\text{weight (kg)}]}{(72) \times [\text{Serum creatinine (mg/dL)}]}$$

For SI units:

$$\text{Cl}_{\text{CR}} \text{ for males (mL/min)} = \frac{[140 - \text{age (years)}] \times [\text{weight(kg)}] \times (1.23)}{[\text{serum creatinine } (\mu\text{mol/L})]}$$

$$\text{Cl}_{\text{CR}} \text{ for females (mL/min)} = \frac{[140 - \text{age(years)}] \times [\text{weight(kg)}] \times (1.05)}{[\text{serum creatinine } (\mu\text{mol/L})]}$$

Calculation of creatinine clearance based on 24-hour urinary creatinine excretion and concurrent serum creatinine levels:

$$\text{Cl}_{\text{CR}} = \frac{C_U \cdot V}{C_{\text{CR}}}$$

Here, C_U is the concentration of creatinine in the urine (mg/dL or $\mu\text{mol/L}$, for SI units), V is the urine volume (in mL per minute of urine produced during the collection period), C_{CR} is the serum creatinine concentration (mg/dL or $\mu\text{mol/L}$, for SI units), and Cl_{CR} is the creatinine clearance in mL per minute.

Appendix III: New York Heart Association (NYHA) Classifications

Class	Description
I	Patients with cardiac disease but without resulting limitations of physical activity. Ordinary physical activity does not cause undue fatigue, palpitation, dyspnea, or anginal pain.
II	Patients with cardiac disease resulting in slight limitation of physical activity. They are comfortable at rest. Ordinary physical activity results in fatigue, palpitation, dyspnea, or anginal pain.
III	Patients with cardiac disease resulting in marked limitation of physical activity. They are comfortable at rest. Less than ordinary physical activity causes fatigue, palpitation, dyspnea, or anginal pain.
IV	Patients with cardiac disease resulting in inability to carry on physical activity without discomfort. Symptoms of cardiac insufficiency or of the anginal syndrome may be present even at rest. If any physical activity is undertaken, discomfort is increased.

This table is an excerpt from the Oxford Textbook of Medicine, 2nd ed. Oxford; New York: Oxford University Press, 1987, p. 2228.

Appendix V: ECOG Performance Status Criteria

ECOG Performance Status Scale

Grade	Descriptions
0	Normal activity. Fully active, able to carry on all pre-disease performance without restriction.
1	Symptoms, but ambulatory. Restricted in physically strenuous activity, but ambulatory and able to carry out work of a light or sedentary nature (e.g., light housework, office work).
2	In bed < 50% of the time. Ambulatory and capable of all self-care, but unable to carry out any work activities. Up and about more than 50% of waking hours.
3	In bed > 50% of the time. Capable of only limited self-care, confined to bed or chair more than 50% of waking hours.
4	100% bedridden. Completely disabled. Cannot carry on any self-care. Totally confined to bed or chair.
5	Dead

18.0 Patient Monitoring and Management Guidelines for Certain Treatment Emergent Adverse Events of Interest (AEOIs)

18.1 Diarrhea

In cancer patients, diarrhea can be debilitating and potentially life threatening, with dehydration, renal insufficiency, and electrolyte imbalances. Pazopanib as a monotherapy has been associated with an increased incidence of diarrhea, which is grade 1 or 2 in the majority with grade 3/4 diarrhea occurring in approximately 4% of subjects. The incidence and severity may increase when administered with other agents known to cause diarrhea.

Early identification and intervention is critical for the optimal management of diarrhea. Please refer to Supportive Care Guidelines for Diarrhea in Appendix I, Section 19.1 for detailed management guidelines. A subject's baseline bowel pattern should be established so that changes in that pattern can be identified. In addition, subjects should be educated on signs and symptoms of diarrhea with instructions to report any changes in bowel pattern to the physician.

Appendix 1: Supportive Care Guidelines

Diarrhea

The NCI CTCAE Version 4.0 criteria for defining diarrhea are provided below.

Toxicity Grade	Diarrhea (includes diarrhea of small bowel or colonic origin and/or ostomy diarrhea)
1	Increase of <4 stools/day over baseline; mild increase in ostomy output compared to baseline
2	Increase of 4-6 stools/day over baseline; IV fluids indicated < 24 h; moderate increase in ostomy output compared to baseline; not interfering with daily living
3	Increase of ≥ 7 stools/day over baseline; incontinence; IV fluids ≥ 24 h; hospitalization; severe increase in ostomy output compared to baseline; interfering with activities of daily living
4	Life threatening consequences (e.g., hemodynamic collapse)
5	Death

Uncomplicated diarrhea is considered mild to moderate and defined as CTCAE Grade 1 to 2 with no complicating signs or symptoms.

Complicated diarrhea is severe and defined as CTCAE Grade 3 or 4 or Grade 1 or 2 with 1 or more of the following signs or symptoms; cramping, nausea/vomiting, \geq Grade 2, decreased performance status, fever, sepsis, neutropenia, frank bleeding, and/or dehydration. If complicated diarrhea goes unrecognized or untreated, it may lead to death.

Experience thus far suggests that, when pazopanib is used as monotherapy, uncomplicated CTCAE Grade 1 or 2 diarrhea may ensue. In rare cases, subjects treated with monotherapy pazopanib may develop

debilitating and potentially life-threatening diarrhea with dehydration, renal insufficiency, and electrolyte imbalances. The pathophysiologic mechanism of diarrhea with pazopanib is not known.

The following broad general management principles are recommended as means by which a subject with diarrhea may avoid more serious complications. Guidelines such as these should never replace sound clinical judgment. Standardized and universal guidelines have been developed by an American Society of Clinical Oncology (ASCO) panel for treating chemotherapy-induced diarrhea [Benson, 2004]. The guidance provided here is a modification of the ASCO guidelines..

[figure not shown]
Early identification and intervention is critical for the optimal management of diarrhea.

- A subject's baseline bowel pattern should be established so that changes in that pattern can be identified.
- Subjects should be educated on the signs and symptoms of diarrhea with instructions to report any changes in bowel pattern to the physician.
- At the initiation of diarrhea, an assessment of frequency, consistency, duration and other symptoms such as fever, cramping pain, nausea, vomiting, dizziness and thirst should be taken to identify subjects at high risk of complications.

Several treatments have demonstrated efficacy in diarrhea management:

- Loperamide, administered as an initial 4-mg dose, followed by 2-mg doses after every unformed stool with a maximum of 16mg per day. This dose and regimen are moderately effective. Continuation of loperamide is suggested until the subject is diarrhea-free for 12 hours. Dose should not exceed a maximum of 8 tablets (16 mg) per day.
- The synthetic octapeptide, octreotide, has been shown to be effective in the control of diarrhea induced by fluoropyrimidine-based chemotherapy regimens when administered as an escalating dose by continuous infusion or subcutaneous injection. In the treatment of chemotherapy-induced diarrhea, octreotide can be administered at doses ranging from 100 μ g twice daily to 500 μ g 3 times daily, with a maximum-tolerated dose of 2000 μ g 3 times daily in a 5-day regimen. However, the effect of octreotide on diarrhea associated with use of pazopanib is unknown.

Figure 1. Generic flow chart for suggested management of Diarrhea

Nausea and Vomiting

Every attempt should be made to control nausea and vomiting in subjects who have emesis and are unable to retain pazopanib.

Routine pre-medication for nausea is not necessary, but symptomatic subjects should be treated with standard anti-nausea/anti-emetic therapy as necessary.

If a subject vomits after taking study medication, the subject should be instructed not to take a replacement dose on that same day. The subject should resume taking pazopanib at the next scheduled dose on the following day. . If vomiting persists then the subject should contact their physician.

To prevent or treat nausea and vomiting standard medications are recommended. Depending upon approved medications in your region, these may include: 5-HT₃ receptor antagonist (granisetron, ondansetron, dolasetron mesylate); NK-1 receptor antagonists such as aprepitant, metoclopramide, phenothiazines (prochlorperazine); corticosteroids, (dexamethasone, prednisone); and cannabinoids (dronabinol).

References:

